The methodology described in detail in field number 14 is summarized. The four premolars due to be extracted for orthodontic reasons will have at least a 1 x 1 millimeter surface flattened with a 169L bur. That surface will be polished with fine and extra fine sandpaper discs. This will improve the evaluation in the dental laboratory, especially of Vickers hardness. A maxillary premolar will be whitened at home with Opalescence 10% CP with PF in 30 sets of subjects and in 10 sets with Opalescence 10% CP without PF for 14 nights. The opposite maxillary premolar will be used as a control (no treatment). The mandibular and collateral premolar of the one that was whitened At-Home it will be whitened in all 40 sets at the office with Opalescent Boost PF 40% HP for a total of 60 minutes (three consecutive times of 20 minutes each). The opposite mandibular premolar to the control in three of the 30 sets of premolars that were treated with PF and in three of the 10 sets of premolars that were bleached without PF will have two narrow bands of Block-Out resin placed on a premolar. The area between the bands will be etched for 15 seconds with Ultra-Etch, a 35% phosphoric acid on the day of the extraction appointment. The extractions will be accomplished 14 days after finishing the whitening At-Home and In-Office procedures. The collected samples will be delivered to TTI for evaluation.

The *in-vivo* treatment of the teeth and the extractions will be performed at UIC. Treatment effects will be evaluated at TTI in Zionsville, Indiana, USA.

7- Keywords:

Demineralization, Teeth whitening, Profilometer, Scanning electron microscope (SEM), Vickers hardness, *in-vivo*.

8- INTRODUCTION OF THE PROJECT:

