The second appointment will occur at least 24 hours after the first appointment. The subject will receive the maxillary whitening tray with a single reservoir for the UR or UL premolar, a tube of Opalescence 10% CP containing or not containing PF whitening gel, and a container for tray storage, when tray is not in use. The tray will be placed in the mouth to ensure a proper fit without interference. During this appointment, the color of that premolar will be taken with VITA Bleachedguide 3-D MASTER shade guide (VITA, Zahnfabrik, Germany). The tray will be placed in the mouth to ensure a proper fit without interference. The subject will be instructed to place a small amount of whitening gel into the individual reservoir for the UR or UL premolar each evening, then carefully place the tray over the teeth, and wipe off the excess gel. The subject will be instructed to wear the bleaching tray for at least 8 hours every night, for 14 days, after brushing their teeth. Each morning after using the tray, the subject will be instructed to brush off the used gel, rinse the tray, store it in the container provided, and brush their teeth with the toothpaste provided. During the 14 days of whitening at home, the subject will be contacted twice by phone or text message to make sure they are using the tray with the whitening gel properly.

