The third appointment will occur on day 15. The subject will return the maxillary whitening tray and will be encouraged to report any concerns with the bleaching treatment or tray usage. During this appointment, the LR or LL premolar and collateral to the one that was bleached at-home will be isolated with OpalDam (Ultradent Products, Inc.) and will be treated with Opalescence Boost PF 40%. The treatment will consist of the application of the gel three separate times, each will remain on the one premolar for 20 minutes, according to the manufacturer's instructions*. If the soft tissue or tooth is sensitive, a soothing gel will be applied to relieve discomfort (Opalescence UltraEZ). Tissue sensitivity usually lasts about thirty minutes and tooth sensitivity usually decreases in two or three days. This appointment will last approximately 90 minutes. During this appointment, an orthodontic separator band or elastic band of 2.5 to 4.5 oz / $\frac{1}{8}$ " to $\frac{1}{4}$ " (depending on interproximal access) will be placed in the gingival area of each premolar to create bone resorption and facilitate an atraumatic extraction. The final color will be taken of the premolar that received 14 days of whitening at-home, as well as the initial and final color of the premolar that will be bleached in-office with VITA Bleachedguide 3-D Master (VITA, Zahnfabrik, Germany); this is to corroborate and document that the teeth were successfully whitened. At this appointment, the subject will be reminded to complete the blood tests required by the UIC oral surgery department since, without these lab tests, the extractions cannot be performed. Therefore, the compensation would not be completed. Also, the subject will be reminded to

continue documenting on the log the brushing at least twice a day for at least one minute each time and will be asked to follow these instructions for the next 14 days.

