Title:

Clinical Evaluation of Enamel Microhardness Using At-Home and In-Office Tooth Whitening Agents

NCT#

07165366

Statistical Analysis:

April 21. 2024

Statistical Analysis

Microhardness was summarized for each active treatment group and for the negative and positive controls. Microhardness comparisons for the treatments and negative controls were performed using ANOVA, with a fixed effect for treatment and a random effect to account for within-subject correlations. Pair-wise tests between treatments were performed using the Sidak method to control the overall significance level. Shade change was summarized by treatment and compared between treatments using Wilcoxon Signed Rank tests (at-home versus in-office) and Wilcoxon Rank Sum tests (at-home with versus without PF). A two-sided overall 5% significance level was used.

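### Is the at-home versus in-office shade test undermined because the two teeth are read at different times after exposure and sit in different arches?

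*Protocol*

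**What the plan says.** The SAP (Statistical Analysis) states that shade change is summarised by treatment and "compared between treatments using Wilcoxon Signed Rank tests (at-home versus in-office"). A rank-sum test compares at-home gel with and without PF, and the overall level is two-sided 5%.

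The protocol fixes the tooth positions in section 6: "A maxillary premolar will be whitened at home with Opalescence 10% CP with PF in 30 sets of subjects", with the other 10 sets receiving the gel without PF on the same kind of tooth, and "The mandibular and collateral premolar of the one that was whitened At-Home it will be whitened in all 40 sets" in the office.

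The shade readings are described in section 14:

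- **At-home tooth, initial:** second appointment. "During this appointment, the color of that premolar will be taken with VITA Bleachedguide 3-D MASTER shade guide".
- **At-home tooth, final, and in-office tooth, both readings:** third appointment, day 15. "The final color will be taken of the premolar that received 14 days of whitening at-home, as well as the initial and final color" (both for the tooth bleached in the office).
- **Purpose:** "this is to corroborate and document that the teeth were successfully whitened".

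No shade reading is described at the fourth appointment on day 29. Sections 11 and 12 list microhardness, profilometry, SEM and the effect of PF as objectives. Shade is not among them.

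**The concern.** Pairing within a subject removes what the two teeth share. It does not remove anything that differs systematically between the at-home tooth and the in-office tooth. Three features do differ in that way:

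- **Arch:** upper for at-home, lower for in-office.
- **Time since last exposure:** the in-office tooth is read in the visit in which it was bleached. The at-home tooth is read at some point after the last overnight tray came off.
- **Interval between the two readings:** about two weeks for at-home, one visit for in-office.

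If any of these shifts shade change on its own, the signed-rank test could reject when the regimens whiten equally, or miss a real difference. The reader would then have a p-value that seems to rank two of the sponsor's products but mixes regimen with arch and timing. The SAP has no term or caveat for this. An obvious repair would be to read both teeth again on day 29, when each is 14 days past treatment.

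**Working it through.** The documents give no effect size, SD or power for shade, so there is no planned figure to reproduce. The check sets the schedule against the quantity tested.

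**1. Arch.** Inputs from protocol section 6. At-home teeth: 30 + 10 = 40, all maxillary. In-office teeth: 40, all mandibular. Every pair (40/40) is upper against lower. The protocol calls the in-office tooth collateral in section 6 and under the third appointment, but contralateral under the first appointment. That affects side, not arch.

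**2. Time since exposure on day 15.** Inputs from section 14.

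- In-office: three applications of 20 minutes, 3 × 20 = 60 minutes, and "This appointment will last approximately 90 minutes". The longest possible lag is 90 − 60 = 30 minutes, approximate because the visit length is.
- At-home: "Each morning after using the tray, the subject will be instructed to brush off the used gel". The lag runs from tray removal to the reading. Neither the hour of the visit nor the order of readings is given. A longer lag than in-office is likely, but its length is an inference.

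This uses the section 14 schedule. Section 17 instead describes day 15 as 14 days after home whitening ended, which conflicts with section 14 and with section 17's own day-29 text. Those passages must be reconciled as a separate, editorial matter.

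**3. What the test compares.** Write B and F for a tooth's initial and final shade, with U for the upper (at-home) tooth and L for the lower (in-office) tooth. The paired quantity is

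D = (F_U − B_U) − (F_L − B_L).

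If upper teeth differ from lower teeth by a constant a, then a enters both F_U and B_U and drops out: a − a = 0. This is exact if the difference is additive on the recorded scale and approximate otherwise. What is left is

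D = regimen difference + any arch-dependent response + any effect of reading sooner after gel + noise.

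The documents give no size or direction for the second and third terms.

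**4. Change window.** Taking the second appointment as day 1: at-home 15 − 1 = 14 days; in-office one visit, at most about 90 minutes. This is essentially the length of each treatment. Each tooth is read before its regimen starts and after it ends, which is a legitimate way to compare regimens of different length.

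**5. What a day-29 reading would do.**

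| Feature | Day-15 readings | With day-29 readings |
|---|---|---|
| Time since exposure | ≤ about 30 min in-office; not stated at-home | 29 − 15 = 14 days, both |
| Upper versus lower | 40/40 pairs | 40/40 pairs |
| Change window, at-home | 14 days | 29 − 1 = 28 days |
| Change window, in-office | one visit | 29 − 15 = 14 days |
| Gap in window | about 14 days | 28 − 14 = 14 days |
| Shade readings | 4 × 40 = 160 | 6 × 40 = 240 (80 more) |

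Only the first row is equalised. The question also changes, from shade at the end of treatment to shade two weeks later.

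**6. Sensitivity, with assumed offsets only.** For 40 pairs, no true regimen difference and a systematic offset of δ SDs of the paired difference, the normal approximation to the rejection rate is Φ(δ√40 − 1.96) + Φ(−δ√40 − 1.96). At δ = 0.2, δ√40 = 1.265 and the result is 0.244. Simulating the signed-rank test itself (4,000 runs, normal differences) gives:

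| δ (assumed) | 0 | 0.1 | 0.2 | 0.3 | 0.5 |
|---|---|---|---|---|---|
| Rejection rate | 5% | 10% | 23% | 45% | 86% |

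The test would respond to an offset if there were one. The table is not evidence that one exists.

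**The case for a change.** The best case for acting is that the SAP does more with shade than the protocol asks of it. The protocol collects shade to document that whitening occurred; the SAP runs a between-regimen test at 5%. Regimen coincides with arch in all 40 pairs, so no analysis of these data can separate the two, and working from each tooth's baseline does not rule out upper and lower teeth responding differently. Relabelling the comparison as descriptive needs no new readings.

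Much of this stands. The attribution limit is real, and a careful report would say that arch and reading time go with regimen, and would give the order and times of readings if they were noted. It does not amount to a change in the plan, because relabelling alters no estimate, no test and no stated conclusion. The protocol states no hypothesis about shade and no claim that one regimen whitens better. The stronger remedy, the day-29 reading, trades one reasonable question for another and corrects only the feature whose importance is least supported. It may also be out of reach: section 17 schedules the visits for August to December 2024, and the SAP is written in the past tense. The documents do not say whether visits are complete.

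**Conclusion.** No change is needed. The observation is accurate but narrow: 40 of 40 pairs set an upper tooth against a lower one, and the in-office tooth is read within about 30 minutes of its last gel, probably sooner after exposure than the at-home tooth. Its force is reduced by the use of change from each tooth's own baseline, and the unequal change windows belong to the regimens being compared. Reading both teeth at the end of treatment is a fair choice for the stated purpose; the later reading would add 80 measurements without giving a clean regimen comparison.

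This rests on three assumptions: the section 14 schedule is the one followed, a baseline arch difference is roughly additive on the recorded shade scale, and shade stays outside the objectives. If the shade result were later used to claim that one regimen whitens better, the limitation would carry more weight. The microhardness analysis does not use shade readings. The with versus without PF shade test compares maxillary teeth read at the same visits, so neither is touched.

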On day 29, 14 days after the at-home whitening treatment was ended and 14 days after the inoffice whitening treatment was accomplished, the subject will return to the UIC oral surgery clinic. Six randomly chosen subjects will have two strips of Block-Out Resin placed on one of their "Control" premolars and the tooth will be etched with 35% phosphoric acid for 15 seconds. On that day, all subjects will return to the clinic, where the maxillofacial surgeon(s) will extract the four premolars that the orthodontist prescribed on all subjects.

The implementation program will be performed on 40 subjects between August and December 2024 in blocks of 5 to 10 subjects at a time.

18- RESEARCH SUSPENSION CRITERIA:

If the subjects decide to withdraw from the research study at any time during the study or develop very uncomfortable tooth sensitivity and decide to stop the study, they may do so without any adverse consequences. However, the subject will not receive the compensation previously

stipulated directly with the administrative department of the UIC's School of Dentistry. Until the final protocol is accepted and authorized by Ultradent, this research study may be suspended in its entirety, or the methodology and/or the number of subjects required may be modified. Any modification of this protocol after it has been approved will be cleared with, and an amendment submitted to, the Bioethics Committee of UIC.

19- Explain the Responsibilities of the researcher, the institution, and the funders:

The investigator must verify that the subject meets the Inclusion and Exclusion Criteria to enter the study. The UIC Department of Orthodontics or other referral entity is responsible for identifying patients who may qualify for the research study by identifying one premolar in each of the four quadrants that require extraction due to relief of crowding to allow orthodontic treatment to continue. The sponsor is responsible for funding all necessary materials used to perform the tooth whitening procedures by the subjects, to conduct the research, and accomplish any follow-up treatment required due to the whitening agents.

20- PROJECT BUDGET:

Ultradent Products, Inc. will fund all necessary materials used to perform the teeth whitening procedures as agreed upon. It is responsible for 1) funding the extractions and compensating for visits to accomplish the tooth whitening procedures by the subjects, 2) compensating the researchers involved in the study, and 3) compensating the university or other referring entities for the use of their facilities and services. Additional materials necessary to accomplish the research must be pre-approved by Ultradent Products, Inc. or [name].

Prepared by:

Dr.

Principal investigator

[contact] [name].

Dr.

Clinical Coordinator

[contact]

[name]

[name].

*Opalescent Boost PF 40% manufacturer's instructions

[figure not shown]
**Extraction protocol

- At least one week prior to the extractions, an orthodontic spacer band or an elastic band of 2.5 to 4.5 oz / $\frac{1}{8}$ " to $\frac{1}{4}$ " (depending on interproximal access) will be placed on the gingival area of each premolar to create bone resorption and facilitate an atraumatic extraction. The orthodontic separator band or elastic will not have contact with the clinical crown, either with the treated enamel area or the proper adaptation of the whitening tray (*photograph 1*).
- On the day of the extractions, a small portion of a tube of Nelaton latex or a small portion of a nitrile glove (depending on interproximal access) will be placed on top of each premolar's tooth crown to protect the treated area during extractions.
- Local anesthetics will be at the discretion of the oral surgeon and the patient's needs.
- Separate the ligament with the appropriate instrument, taking care not to contact the clinical crown or the treated enamel surface. It can be buccal or lingual. It will depend on where is localized the surface more prominent that was treated in case of severe rotation. This will be previously identified before the oral surgeon extracts the teeth to avoid confusion.

- Luxate the tooth with an elevator or appropriate instrument without damaging or scraping the clinical crown or the treated enamel surface of the tooth.
- At the discretion of the surgeon, bone structure can be removed without damaging the treated enamel to facilitate tooth extraction without forceps if necessary.
- It is recommended, if possible, to perform extractions only with elevators (*photograph 2*).
- If final tooth extraction is performed with forceps, care must be taken to protect the clinical crown to avoid damaging the treated enamel of the tooth. Forceps can engage the tooth below the gingival margin along the root surface if necessary. It is recommended to place a portion a small portion of a nitrile glove around the clinical crown to minimize the possibility of trauma (*photographs 3 and 4*).

The oral surgeon will determine and choose the type of anesthesia and all instruments for extractions based on their professional needs and without putting the patient's health at risk.

A personalized clinical diagram will be created for each patient during extractions to avoid confusion about which tooth has been extracted and to ensure that surgeons document any possible incidents during extractions (*example below*).

Extraction chart.

Photograph 1

Photograph 2

Photographs 3 and 4

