Matis et al. in 1996 established that teeth whitening was safe and effective. The concern of some patients and dental practitioners was whether the use of teeth whitening agents harms the teeth. One of the most commonly cited concerns is "Does it soften teeth?" A review of enamel microhardness has been published that identified 55 studies and 166 hardness measurements performed directly after bleaching and after post-treatment (Attin et al. Influence of study design on the impact of bleaching on dental enamel microhardness: A Review Den Mat 25;143;2009). The published article concluded: "The review shows that in those studies, which simulated intraoral conditions as closely as possible (use of human saliva and fluoridation measures, and evaluation after a post-treatment phase), the risk of enamel microhardness decrease due to bleaching treatments seems to reduce as compared to the remaining studies. Nevertheless, more *in-situ/in-vivo* studies are needed to verify the observation". No *in-vivo* designed study has shown that there is a loss of microhardness when bleaching is accomplished. An *in-vivo* designed study published using 15% Carbamide Peroxide as a whitening agent with and without fluoride (Metz et al. Clinical Assessment of 15% Carbamide Peroxide on the Surface Microhardness and Shear Bond Strength of Human Enamel, Op Dent 32:427;2007) stated: "Additionally, there was no statistically significant difference between the treatment specimens compared to the controls in terms of SMH (Surface Microhardness)". Another *in-vivo* published study used 38% hydrogen peroxide as a whitening agent (Cardenaro et al. Effect of Two In-office Whitening Agents on the Enamel Surface *In-Vivo*: A Morphological and Non-contact Profilometric Study Op Dent 33:127;2008), concluded: "No morphological changes were found on the enamel surfaces using non-contact profilometer or SEM analysis". Some researchers have found differences when evaluating enamel surfaces. Therefore, the intention of this study is to determine if there are changes in the enamel surfaces when treating premolars with tooth-whitening agents *in-vivo*.

A common concern with the use of teeth whitening agents is sensitivity to the agents and possible pulpal damage. Research has shown that between 50 and 75% of subjects have some sensitivity.

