The American Academy of Pediatric Dentistry has published a document on tooth whitening that recommends that this treatment be performed by a dentist (Academy of Pediatric Dentistry, 2023). If the soft tissue or tooth becomes sensitive, it has been shown that with the application of potassium nitrate (Opalescence UltraEZ), this sensitivity usually decreases (Tam L.. Effect of potassium nitrate and fluoride on carbamide peroxide bleaching Quintessence Int 32(10):766-70; 2001). Fugaro JO et al. in 2004 concluded that the use of 10% CP can cause minimal short-term

pulpal reactions in about a third of the intact teeth of young people who used the whitening agent; however, if such changes occurred, they were completely reversible. Furthermore, no clinical sensitivity was reported during the two-week treatment period. Also, Fugaro OJ et al. in 2005 concluded that with the use of a 10% CP tooth whitening agent, no increase in the expression of neuropeptides associated with inflammation (substance-P and/or Peptide related to the calcitonin gene) was reported.

9- JUSTIFICATION OF THE PROJECT:

This research proposal will be a confirmatory research study of that published by Metz et al. in 2007 and Cardenaro et al. in 2009, documenting that there is no loss of microhardness when whitening occurs *in-vivo*. It was also recommended by Attin et al., in 2009, in their conclusion that “Nevertheless more *in-situ* and *in-vivo* studies are needed to verify this observation” that enamel microhardness loss decreases the more intraoral conditions are simulated. Metz et al. in 2007 published that there were no statistically significant differences between treatment samples compared to controls in terms of SMH (surface microhardness). Cardenaro et al. in 2008, concluded in her *in-vivo* study that no morphological changes were found on the enamel surfaces using a non-contact profilometer or SEM analysis. There are no known studies, to our knowledge, of the effect of PF compared with non-PF treated surfaces on the physical characteristics of enamel.

The identification, treatment, and extraction of the teeth to be whitened will be performed at the UIC and other approved entities. TTI will study the collected *in-vivo* samples from Mexico City and will also perform simultaneous studies *in-situ*.

10- PROJECT HYPOTHESIS:

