Some teeth whitening agents are acidic, and pH values below 5.5 have been shown to cause demineralization of tooth structure. This may be a reason some studies have shown that a loss of microhardness occurs when using some acidic tooth-whitening products. In a study by Attin et al. 2009, when samples were kept in a “non-demineralizing solution”, 47% of studies showed no reduction in sample microhardness; when they were kept on “artificial saliva,” 46% of studies showed no reduction; when kept in “human saliva,” 78% of studies showed no reduction. However, after post-treatment, 100% of studies showed no reduction in microhardness when samples were kept in “human saliva.” When studies were conducted “fluoride-free” and microhardness measurements were accomplished, 46% showed no reduction in microhardness; when “fluoride” was used as part of the conditions of the study, 86% of the studies showed no reduction in microhardness. When the study design was *in-vitro*, 48% of the studies showed no reduction in the microhardness; when the study design was *in-situ/in-vivo*, 64% showed no reduction in microhardness. When whitening agents have a neutral pH and enamel samples are maintained in human saliva, there is no loss of hardness or changes in the enamel surface, according to a systematic review and meta-analysis accomplished in New Zealand. (Zanolla J. et al. Influence of tooth whitening on the microhardness of tooth enamel: a systematic review and meta-analysis. Aust Dent Jour 62:276-282;2017).

14- PROJECT METHODOLOGY:

Methods and materials

This study consists of 40 patients requiring the extraction of four permanent first or second premolars for orthodontic reasons. Patients will be recruited from the Universidad Intercontinental (UIC) Graduate Program in Orthodontics, the Universidad Autonoma de Mexico (UNAM) Graduate Program in Orthodontics, and private orthodontist dental offices in the city of Mexico. Patients who identify as needing extraction of the four first or second permanent premolars and who meet the following inclusion criteria will be invited to participate in the study.

Inclusion criteria:

- Have the four premolars in different quadrants that their orthodontist recommends be extracted.
- The premolars to be extracted should have prominent facial surfaces.
- Willing to have the four premolars slightly flattened and smoothed.
- Willing to have all four premolars extracted for orthodontic reasons.
- Between 12 and 35 years of age.

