- Willing to attend four appointments.
- Willing to wear a custom-made whitening tray during the evening when they sleep.
- Willing to have their premolars bleached with In-Office and At-Home bleaching agents and one of their teeth that will be extracted treated with phosphoric acid.
- Willing to sign a consent form (parents must co-sign if they are under 18).
- Willing to discontinue active orthodontic treatment during whitening treatment.
- Willing to brush at least twice a day with fluoridated toothpaste provided during the study.

Exclusion criteria:

- Restorations or visible cavities in the teeth to be extracted.
- The presence of visible intraoral structural defects or pathology.
- Use of over-the-counter or professionally prescribed whitening agents in the past six months.
- Teeth with tetracycline staining.
- History of any medical illness that may interfere with the study or require special considerations.
- Pregnant or lactating women.
- Not willing to do the blood tests (biometrics hematic, prothrombin, and thromboplastin) prior to extractions (a legal requirement of the Oral Surgery Department of the UIC).

Treatment plan:

The study will be approved by Ultradent Products, Inc. and the Health Sciences Divisional Area Bioethics Committee, which is the equivalent of the Institutional Review Board (IRB) of UIC before any patients will be evaluated for eligibility to enter the study.

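### Section 18, as worded, withholds the agreed compensation from a subject who stops early, including for very uncomfortable sensitivity; it should pay for each appointment attended

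*Protocol*

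**What the plan says.** Section 18 covers two kinds of subject: those who withdraw at any time, and those who develop very uncomfortable sensitivity. Of the latter it says that if they "decide to stop the study, they may do so without any adverse consequences". It then continues: "However, the subject will not receive the compensation", meaning the sum previously agreed with the administration of the School of Dentistry. It gives no amount, no schedule and no exception.

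Three other places bear on payment:

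- Section 14, third appointment: without the blood tests the extractions cannot go ahead. "Therefore, the compensation would not be completed".
- Section 20: the sponsor's responsibilities include "compensating for visits to accomplish the tooth whitening procedures by the subjects".
- Section 14, on risks and compensation: payments pass through the school's administration, and the sponsor is responsible for treatment that subjects need because of the whitening.

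On who is exposed and how often sensitivity occurs, the inclusion criteria set the age range at "Between 12 and 35 years of age", with a parent co-signing for those under 18. Section 8 states: "Research has shown that between 50 and 75% of subjects have some sensitivity". It also cites a study of 10% carbamide peroxide in which "no clinical sensitivity was reported during the two-week treatment period".

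**The concern.** Section 18 is the only provision in the readable text for stopping on grounds of tolerability, and it relies on the subject's own decision. A promise of no adverse consequences, followed at once by loss of payment, weakens that provision. Someone in discomfort, possibly an adolescent, has a monetary reason to keep wearing the tray or to accept the in-office session. Parental co-signature governs entry to the study and does not alter the incentive to continue.

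A subject who stops in the home phase has also already given something. At the first appointment all four premolars are flattened with a bur and polished (Section 17). On the literal reading, that subject is paid nothing for it.

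Only subject protection is at stake. The whitened teeth are one maxillary premolar (at home) and one mandibular premolar (in-office), both due for extraction.

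**Working it through.** The plan gives no payment figure to reproduce, so the check is mainly a reading of the passages side by side, with simple arithmetic to show what can and cannot be sized.

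**1. The Section 18 sentence.** It opens with a contrastive word straight after the no-consequences promise, so it qualifies that promise. Its subject is the person just described, which includes the one who stops for sensitivity. Read literally, that person receives none of the agreed compensation.

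**2. The other payment wording.** The Section 14 phrase about compensation not being completed fits payment in stages, with a last part tied to the extractions. Section 20 refers to visits, which fits payment per visit. On either footing, Section 18 could mean only that the unpaid remainder is withheld. Neither passage says so, and neither says what a subject who stops keeps.

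**3. What a stopper would be paid for under each reading.** Appointment 1 is selection, 2 is tray delivery, 3 is the in-office session on day 15, and 4 is extraction on day 29. Section 20 speaks of visits for the whitening procedures, and no whitening takes place at appointment 1. A per-visit reading may therefore exclude it.

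| Stop occurs | Attended | Literal reading | Whitening visits only | Every visit |
|---|---|---|---|---|
| Home phase | 2 of 4 | 0 | 2 − 1 = 1 | 2 |
| After the day-15 session | 3 of 4 | 0 | 3 − 1 = 2 | 3 |

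**4. When the incentive can act.** Home wear is at least 8 hours a night for 14 nights, a minimum of 14 × 8 = 112 h. Wear remaining after night n is (14 − n) × 8 h:

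- after night 1: 13 × 8 = 104 h
- after night 13: 1 × 8 = 8 h
- after night 14: 0 h

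In each case the in-office session, 3 × 20 = 60 minutes of 40% hydrogen peroxide, is still to come. After day 15 no whitening is scheduled, so the incentive has no further whitening to prolong. It acts mainly in the home phase and ends with the in-office session. These hours show when it applies; they do not measure harm.

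**5. How many subjects.** Section 8's range for any sensitivity gives 40 × 0.50 = 20 to 40 × 0.75 = 30 of the 40 subjects. The cited 10% carbamide peroxide study reported none, but every subject here also receives 40% hydrogen peroxide, so that study does not settle the lower end. The relevant number is those who would stop for very uncomfortable sensitivity but continue for the money. Neither that number nor the sum at stake is in the documents, so the effect cannot be quantified.

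**The case against.** The strongest reply is that Section 18 is an ordinary completion-payment rule. It covers every withdrawal, not sensitivity in particular. It refers to terms agreed elsewhere, and the consent pages where those terms may sit are not in the reviewed copy. The other payment wording leans towards staged or visit-based payment. The subject is also not left without support: withdrawal is free at any time, soothing gel or a potassium nitrate syringe is available, subjects are contacted twice in the home phase, the sponsor pays for whitening-related treatment, and the Bioethics Committee must approve the study first.

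Much of this stands. A reader might infer that total forfeiture is established, or that the trial has no rule on pay for attended visits; the documents support neither. A reader might also infer that 20 to 30 subjects are affected, but that range counts any sensitivity. Nor do the documents show that the clause was aimed at adverse events.

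The reply does not remove the wording itself. The safeguards concern care and relief, not payment. The one readable sentence that governs a tolerability stop still denies compensation on its face, without exempting sensitivity or visits already made.

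**Conclusion.** The point holds as a small subject-protection improvement. In the readable text, Section 18 makes compensation depend on completion, even for a subject who stops because of very uncomfortable sensitivity. This rests on the literal reading of one sentence. Staged payment remains possible, and the consent pages could confirm it. The sum, the number of subjects and the strength of the incentive are all unknown.

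A reader might go further and suppose that subjects continuing through discomfort would distort the microhardness comparison. Nothing in the documents supports that, and no such effect is claimed.

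**What to change.** Replace the non-payment sentence in Section 18 with: *A subject who stops for any reason, including tooth sensitivity, is paid for each appointment attended; only payment for appointments not attended is withheld.* Make the consent wording match.

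The cost is one amendment through the Bioethics Committee route that Section 18 already provides, plus some partial payments. Those may include the selection appointment, which Section 20 may not cover at present, so the change could slightly enlarge an existing per-visit arrangement. The incentive to complete becomes a little weaker but does not disappear, since later appointments still carry pay.

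Section 17 planned the work for August to December 2024. If it is finished, the equivalent step is to check whether anyone who stopped early was refused pay for appointments attended, and to correct the wording for future studies.
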